5.6 Geographical device considerations

5.6.1 For EU sites:

In Europe, any commercially available (CE Marked) Portico valve, delivery system, loading system or other accessory may be used in this trial according to its labeling (IFU). It is the responsibility of the investigator to ensure that the devices:

- Will be used according to the IFUs
- Will be accounted for together with the patient's contact details in the Patient Identification Log (PIL)

5.6.2 For Australian and Canadian sites:

Portico devices utilized in this trial in Canada and Australia may be investigational and used according to their respective regulatory submission documents. These products may continue to be used in the trial upon commercial release in each country. It is the responsibility of the investigator to ensure that the devices:

- Will be used according to the IFUs/IB
- Will be accounted for together with the patient's contact details in the Patient Identification Log (PIL)
- Will be traced using the appropriate traceability documentation (Note: this requirement applies to investigational devices only)

5.6.3 Investigational device accountability for Australian and Canadian sites:

Access to devices which haven't received regulatory approval shall be controlled and these devices shall be used only in the clinical investigation and according to the CIP and IFU/IB.

The sponsor shall keep records to document the physical location from shipment of these devices to the investigation sites until use, return or disposal. The Principal Investigator or authorized designee shall keep records documenting the date of receipt, the unique identification or lot number of each investigational device, the patient identification, the date of use, the expiry date, the date on which the investigational device was returned/explanted from the patient (if applicable) and the date of return of unused, expired or malfunctioning investigational devices (if applicable).

5.7 Hospital heart team

The “Heart Team” is a multi-disciplinary team involving at least (but not limited to):

- Two physicians of which one should be a cardiologist or an interventional cardiologist and a cardiac surgeon
- Any other relevant function such as an imaging specialist or a TAVI nurse.

The objective of the Heart Team is to review and interpret patient’s clinical data in order to obtain a consensus on the optimal treatment strategy for each patient. The heart team will be responsible for ensuring and documenting patient’s eligibility to receive a Portico Valve.

Investigational sites will use their standard documentation to report the heart team’s recommendations, including the members of the heart team, for each patient prospectively or retrospectively enrolled in the study. This instruction only applies to Cohort A.

In certain circumstances, it might be decided to send relevant clinical data (such as echocardiogram, CT/MRI or Angiogram) out of the hospital for further analysis to determine if patient’s valve anatomy is suitable for participation in the clinical investigation. If required, an authorization form to release medical information outside the hospital is available for sign-off by the patient.

5.8 Patient screening

Patient candidates for a TAVI procedure or who already received a Portico Valve as part of a SJM-sponsored regulatory or first-in-human trial can be screened by any member of the investigational team trained on the CIP and delegated to do so. Patients who do not meet the inclusion/exclusion criteria will not be eligible to participate in this clinical investigation. Patients meeting the inclusion/exclusion criteria will be fully informed about the clinical investigation and asked to participate. In case a patient agrees to participate, a duly signed and dated Patient Informed Consent (PIC) will be obtained.

All patient candidates for a TAVI procedure should be accounted for and documented on the screening and enrollment log in an anonymous fashion. This log should be kept up to date throughout the clinical investigation by the principal investigator or his/her authorized designee.

The investigational sites involved in previous SJM-sponsored regulatory or first-in-human trials involving the Portico Valve will also be asked to contact the patients who participated and invite them to participate in this extended follow-up clinical investigation. These patients shall be accounted for in a separate screening and enrollment log.

5.9 Point of enrollment

Patients will be considered enrolled in the clinical investigation once they have provided signed and dated written Informed Consent (refer to section 7.2 for the Informed Consent Process).

Once enrolled, a patient is expected to comply with the required clinical investigation visits and assessments. All patients enrolled in the clinical investigation (including those withdrawn or lost to follow-up) shall be accounted for and documented on the Patient Identification Log, assigning an identification code linked to their names, alternative identification or contact information. This log shall be kept up to date throughout the clinical investigation by the principal investigator or his/her authorized designee. Since patient privacy and confidentiality of data must be maintained throughout the clinical investigation, this log will remain on site.

5.10 Inclusion and Exclusion Criteria

The following inclusion and exclusion criteria will be used to determine a patient's enrollment eligibility in the clinical investigation. Candidates for this clinical investigation must meet all the inclusion criteria and none of the exclusion criteria.

5.10.1 Inclusion Criteria

All candidates will meet the following inclusion criteria:

1. Patient has signed the Patient Informed Consent prior to participating in the clinical investigation.
2. Patient has been referred for a Portico Valve implant as per Heart Team decision **or** patient has received a Portico Valve as per participation in an SJM sponsored regulatory or first-in-human trial.
3. Patient has senile degenerative aortic valve stenosis confirmed by echocardiographically derived criteria*:
 - An initial aortic valve area (AVA) of less than or equal to (\leq) 1.0 cm² (or indexed EOA less than or equal to (\leq) 0.6 cm²/m²)
AND
 - A mean gradient greater than ($>$)40 mmHg or jet velocity greater than ($>$)4.0 m/s or Doppler Velocity Index less than ($<$)0.25.

If the mean gradient is $<$ 40 mmHg and left ventricular ejection fraction (LVEF) $<$ 55%, then the site may as well perform a dobutamine stress echo to see if the mean gradient increases to $>$ 40 mmHg.”

(Baseline measurement taken by echo within 6 months of index procedure.)

4. Patient has a life expectancy more than ($>$) 12 months.*

For patients enrolled in a French site:

5. Patient is at high risk for surgery as demonstrated by a Logistic EuroSCORE equal or more than (\geq) 20 and/or a Society of Thoracic Surgeon (STS) mortality risk score of more than ($>$) 10% and/or by clinical judgment of the Heart Team based on the individual risk profile (comorbidities).

**Not applicable for a patient who has received a Portico Valve as per participation in an SJM sponsored Regulatory or First-In-Human trial.*

[figure not shown]
5.10.2 Exclusion Criteria

Candidates will be excluded from the clinical investigation if any of the following criteria is present:

1. Any case in which the Portico Valve would not be indicated for the patient as per current IFUs (i.e. any “off-label” use).
2. Patient has any other aortic valve than tricuspid one.
3. Patient has a prosthetic valve or ring in the aortic position.
4. Patient needs a concomitant structural heart procedure.
5. Patient is unwilling or unable to comply with all clinical investigation-required follow-up evaluations.
6. Patient is pregnant.

The figure below summarizes the screening, enrollment and eligibility assessment scheme for Cohort A.

Figure 3: Patient’s eligibility assessment scheme (Cohort A)

*If required, an Authorization form to release medical information to be signed

5.10.3 Additional considerations

In case of patient's death and/or occurrence of adverse events (serious or not) prior to the Portico valve implant, these events will be reported separately and will not be taken into account in the study endpoints reporting.

In case a patient signed the PIC but would not receive a Portico Valve, reasons for patient not receiving a Portico Valve will be reported separately and will not be taken into account in the study endpoints reporting. Patient will then be withdrawn from the study. However, if the Portico valve or delivery system entered the patient's body but was not successfully implanted, the patient should continue in follow-up until 30 days or until all adverse events associated with the Portico device or procedure are resolved (whichever occurs first). Possible reasons for patient not receiving a Portico Valve are listed below but are not limited to:

- Screening failure (patient did not meet all inclusion criteria or/and meet one exclusion criteria) before the index procedure
- Investigator's decision to withdraw the patient before the procedure
- Adverse event affecting patient's eligibility to TAVI
- Procedural exclusion
- Unsuccessful implant attempt
- Consent withdrawn, lost to follow-up or death before the procedure

[figure not shown]
6 Procedures

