5.3.2 Secondary Endpoints

- Evaluation of the VARC-2¹⁹ defined event rates at 30 days, 1 year and annually through 5 years post implant. Definitions are detailed in Appendix D: VARC 2 Endpoints Definitions.
 - All-Cause Mortality
 - Cardiovascular Mortality
 - Myocardial Infarction
 - Stroke (disabling and non-disabling)
 - New or worsened conduction disturbances and cardiac arrhythmias (including pacemaker implantation rate at 30 days and new-onset atrial fibrillation (AF))
- Evaluation of the VARC-2¹⁹ defined event rates at 30 days from the index procedure.
 - Vascular access site complication (major and minor)
 - Bleeding (life-threatening, major and minor)
 - Acute kidney injury

- Prosthetic valve function at 30 days, 1 year and annually through 5 years post implant. (Includes prosthetic valve stenosis and prosthetic valve regurgitation).
- Clinical benefit endpoints at 30 days, 1 year and annually through 5 years post implant (if available)
 - NYHA functional classification
 - 6 Minute Walk Test (6MWT)
 - Quality of life measured with EQ-5D questionnaire through 1 year post-implant
- Evaluation of the TAVI-related resource utilization through hospital discharge (e.g. index procedural hospital/physician resources)
- Interim reporting at 30 days and 1-year all-cause mortality data may be performed on a subset of patients and compared with an appropriate external comparator. The results will be presented to appropriate agencies in France and in other countries where it will be deemed necessary for reimbursement purposes.

NOTE: Should new VARC or ESC Guidelines be published, endpoint analysis would be adjusted accordingly and analyzed to the extent that the previously gathered data supports the analyses based on the most current guidelines.

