6.2.3. Portico Valve Implant visit - Index procedure (Cohort A only)

The medical team performing the TAVI procedure will typically consist of:

- An interventional cardiologist or a cardiac surgeon at the site will perform the procedure according to local guidelines.
- A second operator (a cardiac surgeon or a cardiologist) may be present during the procedure as needed.
- An anesthesiologist and/or a perfusionist as needed.

The implanting physician should be trained according to SJM Portico training program prior to implant of the Portico Valve.

NOTE: The above medical team members do not need to be trained on the protocol if they only perform the Portico Valve implant and no other study related tasks.

NOTE: Anticoagulation is left to the physician’s discretion” or should be established as with any other biological valve implantation, considering risks and benefits for the patient.

At least one device may be deployed in every patient who has signed the PIC and is not procedurally excluded. Although not recommended, if a physician determines it is in the best interest of the patient to have a second device placed, a patient may receive an additional device.

The procedure visit will consist of the following steps:

- Pre-implant (access preparation)
- Implant (valve deployment)
- Aortic regurgitation assessment combining angiography, echocardiography and hemodynamic approach
- Implant depth and prosthesis-patient mismatch assessment
- Post-implant (access closure)
- Medication assessment
- Device implantability assessment
- Adverse events assessment
- Device Deficiency assessment
- Resource utilization assessment

It is strongly recommended to follow the peri-procedural instructions for the assessment of aortic regurgitation and implant depth as mentioned in Appendix I. However, failure to follow these instructions will not be considered a protocol deviation.

Procedural Exclusion

During the procedure, the implanting physician may determine the implantation of the Portico Valve is either not feasible or not in the best interest of the patient. Reasons for procedural exclusion may include, but are not limited to, anatomy that is not suitable for implantation, inability to gain access, ventricular arrhythmia, or any other contraindication. Any patient that does not have a delivery system enter his or her body will be considered “procedurally excluded.”

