9.4 Secondary endpoint analysis

The secondary endpoint analysis will include both cohorts but results will be presented separately.

All safety secondary endpoints will be estimated using non-parametric survival analysis, and the data will be presented with the aid of Kaplan-Meier curve. The time to event will be defined as from the implant date to the first occurrence of the event for the patients who experienced the event, or to the last documented contact date for the patients without the event.

All safety secondary endpoints will be reported at 30 days, 1 year, 2 years, 3 years, 4 years and 5 years post implant, as recommended by VARC 2.

Note: Safety events which occurred prior to the index procedure will be reported separately and will not be included in the safety secondary endpoints reporting.

All continuous secondary endpoints will be summarized with the number of non-missing data, mean \pm standard deviation, median and range (minimum – maximum).

All categorical secondary endpoints will be tabulated with number of occurrence, and the percentage.

Generalized linear mixed model will be used to assess the evolution of the NYHA class at baseline, 30 days, 1 year, 2 years, 3 years, 4 years and 5 years post implant.

General linear mixed model will be used to evaluate the improvement for the QOL at baseline, 30 days, 1 year, 2 years, 3 years, 4 years and 5 years post implant.

Other secondary endpoints analysis will be described in a separate statistical analysis plan. This document will be available upon request.

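### Section 9.1 does not place patients whose implant failed after the device entered the body: in effect they drop out of every endpoint, and the protocol's day-30 follow-up rules for non-implanted patients conflict

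*Combined protocol and SAP*

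**What the plan says.** - **5.10.3.** Of deaths and adverse events: "prior to the Portico valve implant, these events will be reported separately and will not be taken into account in the study endpoints reporting". A consented patient who receives no valve is withdrawn. The exception is a patient whose body the valve or delivery system entered without a successful implant. That patient stays in follow-up to 30 days or until device- or procedure-associated events resolve, whichever is first. The list of reasons for not receiving a valve gives procedural exclusion and unsuccessful implant attempt as separate items.
- **6.2.3.** A patient is procedurally excluded if no delivery system entered the body. Data on these patients are collected through the 30-day follow-up, and they are then withdrawn.
- **9.1.** Three groups leave the analysis dataset: those ruled out before the index procedure; those who started the procedure, received no valve and are procedural exclusions; and those who died, were lost or withdrew consent before the procedure.
- **9.2.1 and 9.3.** The primary endpoint concerns valve recipients, with survival time counted from the implant date.
- **9.4.** For the safety secondary endpoints, "The time to event will be defined as from the implant date to the first occurrence of the event". The section adds that "Other secondary endpoints analysis will be described in a separate statistical analysis plan".
- **5.2.2 and 5.3.2.** The secondary objective covers peri-procedural safety and names the Delivery System. Vascular complications, bleeding and kidney injury are "defined event rates at 30 days from the index procedure".
- **7.3.2 and 7.4.1.** Safety surveillance ends when participation ends. All deaths are to be reported, with use of national death registries.

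**The concern.** Patients in whom the device entered the body but no valve was implanted have been exposed to the delivery system and to the procedure. If they appear in no endpoint, the 30-day mortality, bleeding, vascular and stroke rates describe successful implants only. Such rates can look favourable and cannot be set beside rates per attempt. The optional external comparison of 30-day and 1-year mortality in 5.3.2 states no denominator, so the mismatch could pass unnoticed there.

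The follow-up text adds to this. The group with more device exposure may leave before day 30, while 6.2.3 keeps collecting data through day 30 on patients no delivery system entered. Data that sites were not asked to collect cannot be recovered at the analysis stage.

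**Working it through.** **Step 1: the plan's own figure.** With p = 0.221 and half-width h = 0.033 (limits 18.8% and 25.4% in 9.2.1), n = 1.96² × 0.221 × 0.779 / 0.033² = 607.3, rounded up to the stated 608. This is the binomial form rather than Peto's, a difference that does not bear on this point. Recruitment is 608 / (0.779 × 0.90) = 867.2, close to the stated 866. Neither figure depends on what follows.

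**Step 2: the sections side by side.**

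| Patient | Exclusion in 9.1 | Implant date | Follow-up in 5.10.3 | Follow-up in 6.2.3 |
|---|---|---|---|---|
| Procedure started, no delivery system entered | Procedural exclusion | None | Withdrawn | Data through 30-day follow-up, then withdrawn |
| Device entered, no valve implanted | None, under the 6.2.3 definition | None | 30 days or resolution of related events, whichever is first | Not covered by the procedural-exclusion rule |
| Valve implanted | None | Yes | Scheduled visits | Scheduled visits |

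The second row is the gap. By 9.1 these patients are not removed. By 9.3 and 9.4 they have no time zero. By 9.2.1 they are outside the primary endpoint. Under 5.10.3 none of their events can fall after an implant. They leave every endpoint without a rule that says so. The first row shows a second conflict: 5.10.3 and 6.2.3 give different follow-up for the same patients.

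**Step 3: possible size at 30 days.** The documents give neither a failure rate nor mortality after failure, so every input here is an assumption, including the use of 866 as the number of attempts.

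Rate per attempt = (1 − f) × m_implanted + f × m_failed, so the shift is f × (m_failed − m_implanted).

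- Patients: 866 × 0.01 = 8.7 to 866 × 0.05 = 43.3.
- Deaths outside the implanted-only rate: 8.66 × 0.15 = 1.3 to 43.3 × 0.30 = 13.0.

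| m_implanted | f = 1%, m_failed = 15% | f = 5%, m_failed = 30% | 95% half-width, n = 866 |
|---|---|---|---|
| 3% | +0.12 | +1.35 | 1.14 |
| 5% | +0.10 (5.10%) | +1.25 (6.25%) | 1.45 |
| 8% | +0.07 | +1.10 | 1.81 |

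Shifts and half-widths are in percentage points. The 5% half-width is 1.96 × √(0.05 × 0.95 / 866) = 1.45 points. If m_failed equals m_implanted, the shift is zero.

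**Step 4: 1 year, for scale only.** With f = 1% and m_failed = 30%, the shift from 22.1% is 0.01 × 7.9 = 0.08 points. With f = 5% and m_failed = 50%, it is 0.05 × 27.9 = 1.40 points, giving 23.5%, inside the planned 18.8-25.4%.

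**The case against.** The strongest reply is that the outcome is already determined. The question concerns implanted patients (5.2.1, 5.3.1, 9.2.1), times run from an implant date, and 5.10.3 withdraws patients without a valve. The words in 9.1 about circumstances of the procedure or physician judgment can be read to cover every non-implanted patient. Even the secondary objective in 5.2.2 speaks of the valve as implanted, and an attempted-implant set may already exist in the separate statistical analysis plan, which is not among the documents.

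Much of this stands. It settles the primary analysis and makes the request a supplement to it. It does not close the gap in 9.1: the wider reading contradicts the definition in 6.2.3 and the separate listing in 5.10.3. Nor can a separate plan supply day-30 data that the protocol lets sites not collect.

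On follow-up, early exit requires that related events have resolved, and 7.4.1 asks for all deaths to be reported. A reader might infer that deaths after early withdrawal go unreported. The documents do not support that as a flat statement. They leave open whether 7.4.1 reaches withdrawn patients, given that 7.3.2 ends surveillance with participation.

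A reader might also infer that 5.10.3 drops access-phase bleeds or vascular injuries in implanted patients, because the 9.4 Note uses another cut-off: "Safety events which occurred prior to the index procedure will be reported separately and will not be included in the safety secondary endpoints reporting". The documents do not support this either. Table 3 includes pre-implant access information under the valve implant activity, the 6.2.3 heading equates the implant visit with the index procedure, and time is counted in days. That difference is one of terms.

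**Conclusion.** The point holds as minor to moderate. The protocol does not say where failed implants with device entry belong, in effect leaves them out of every endpoint, and gives conflicting follow-up to day 30 for non-implanted patients. The peri-procedural safety rates are then conditional on a successful implant.

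The size is not known. With 5% 30-day mortality in implanted patients, the assumed ranges give a shift of 0.1 to 1.25 points, and only the upper end is material against a half-width of 1.45. These figures illustrate scale and are not evidence of bias in this study.

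The documents do not support a stronger conclusion that the primary mortality analysis is wrong or should move to all attempts: implanted-only mortality is the declared question. Nor do they support the claim that no attempted-implant analysis is planned, since the separate statistical analysis plan was not available.

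**What to change.** 1. Keep the implanted-only primary analysis and all time origins in 9.3 and 9.4. Moving the origin in 9.4 alone would give 1-year mortality, which is both a primary and a secondary endpoint, two stated origins.
2. In 9.1, use the 6.2.3 definition of procedural exclusion and state where failed implants with device entry belong.
3. Add a supplementary Cohort A attempted-implant table, with the device-entered subset shown, of 30-day mortality and VARC-2 events counted from the procedure date. Present it beside the implanted-only results. If the separate statistical analysis plan already has such a table, refer to it in 9.1.
4. Reconcile the follow-up wording of 5.10.3 and 6.2.3 so that day-30 status is available for every patient in that table, and say whether the death reporting in 7.4.1 applies after withdrawal.
5. Optionally, as an editorial change, align the cut-off term in 5.10.3 with that in the 9.4 Note.

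**Cost.** Wording changes, one extra set of tables, and day-30 status contacts for perhaps 9 to 43 patients under the assumed 1-5% failure rate. The follow-up wording may need ethics committee notification or approval (section 12). The supplementary rates may look slightly less favourable. The primary objective, endpoint, analysis and sample size do not change.

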5.2.2 Secondary Objective

The secondary objectives of this clinical investigation are to assess the peri-procedural and long-term performance and safety profile of the Portico Valve implanted, using the Delivery System and the Loading System, in patients with severe symptomatic aortic stenosis.

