Data will be collected on these subjects from the Baseline through the 30-day follow-up, including reason for exclusion and collection of possible adverse events.

The patient should then be withdrawn from the clinical investigation.

Following the procedure, the delivery and loading systems should be securely disposed as per hospital requirements for hazardous materials. If there are any concerns noted with the delivery system, loading system, or valve during the procedure, they should be returned to SJM per instructions provided in Appendix K: Explant, Return, and Analysis of Valve and Appendix L: Instructions for device return - Large and Small Kits.

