6.2.4. Pre-Discharge visit (Cohort A only)

The pre-discharge visit will take place at the time of hospital discharge or within seven days after the index procedure, whichever occurs first. If the patient is expected to be discharged over the weekend, the discharge tests may be completed on the last week day prior to discharge. The assessment will include:

- Physical assessment
- Blood sample (between day 2 to 4 Post-implant or at discharge whatever occurs first) to obtain Hemoglobin, Creatinine and Troponin values
- 12 lead ECG (within 24hrs Post-implant and at hospital discharge but no later than 7 days Post-implant, whatever occurs first).
- Medication assessment
- Echocardiography (if a post-procedure echo has been done within 24 hours prior to discharge, an additional discharge echo is not required)
- NYHA functional classification
- QoL questionnaire (EQ-5D)
- Modified Rankin Scale
- Adverse events assessment
- Device Deficiency assessment
- Resource utilization assessment

6.2.5. 30 Day follow-up visit (Cohort A only)

The 30 Day visit will take place at 30days (-7 days, +14days) after the index procedure, and will include:

- Frailty Assessment by means of the following components: 5 meters walking time, grip strength, wasting and malnutrition (including blood sample to obtain Serum Albumin value) and cognitive impairment or dementia (via MMSE)
- Physical assessment
- 12 lead ECG
- Medication assessment
- Echocardiography
- NYHA functional classification
- QoL questionnaire (EQ-5D)

- 6MWT
- Modified Rankin Scale
- Adverse events assessment
- Device Deficiency assessment
- Permanent Pacemaker Control (if applicable)
- Resource utilization assessment

6.2.6. 1 Year follow-up visit (Cohort A only)

The 1 Year visit will take place at 365 days (\pm 90days) after the index procedure, and will include:

- Frailty Assessment by means of the following components: 5 meters walking time, grip strength, wasting and malnutrition (including blood sample to obtain Serum Albumin value) and cognitive impairment or dementia (via MMSE)
- Physical assessment
- 12 lead ECG
- Medication assessment
- Echocardiography
- NYHA functional classification
- QoL questionnaire (EQ-5D)
- 6MWT
- Modified Rankin Scale
- Adverse events assessment
- Device Deficiency assessment
- Resource utilization assessment

6.2.7. 2 Year follow-up visit

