Adverse device effect that has resulted in any of the consequences characteristic of a serious adverse event.

Unanticipated Serious Adverse Device Effect (USADE)

A serious adverse device effect which by its nature, incidence, severity or outcome has not been identified in the current version of the risk analysis report.

Anticipated Serious Adverse Device Effect (ASADE)

A serious adverse device effect which by its nature, incidence, severity or outcome has been previously identified in the risk analysis report.

Device Deficiency (DD)

An inadequacy of a medical device with respect to its identity, quality, durability, reliability, safety or performance. Device Deficiencies include malfunctions, use errors and inadequate labeling.

7.3.2. Procedure for assessing, recording and reporting adverse events, adverse device effects, serious adverse events, serious adverse device effects and device deficiencies

Safety surveillance and reporting will be done for all patients enrolled in this investigation.

Safety surveillance within this clinical investigation and safety reporting, both performed by the investigator, starts as soon as the patient is enrolled in this clinical investigation (date of signature of the informed consent). The safety surveillance and the safety reporting will continue until the last investigational visit has been performed or the patient is deceased or the patient/investigator concludes his participation into the clinical investigation.

NOTE: If an adverse event is documented at the patient's last follow up visit, both the notification and follow-up information on the AE eCRF are to be provided to the sponsor.

- All Serious Adverse Events (regardless of their relationship with the device or the procedure) and all Adverse Device Effects (serious or non-serious) are to be documented and reported to the sponsor maximum 3 calendar days after becoming aware of the event.
- All Device Deficiencies, that could have led to a Serious Adverse Device Effect,
 - if either suitable action had not been taken;
 - if intervention had not been made or
 - if circumstances had been less fortunate,are to be documented and reported to the sponsor maximum 3 calendar days after becoming aware of the event.
- Non-serious adverse events documentation and reporting are limited to cardiovascular and neurovascular events; they all have to be reported regardless of their relationship with the device or the procedure.

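### Sections 5.10.3 and 6.2.3 conflict on follow-up of patients who receive no valve, and 5.10.3 lets device-exposed patients leave before day 30 depending on their own adverse-event course

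*Combined protocol and SAP*

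**What the plan says.** Four parts of the protocol bear on patients who consent but do not receive a valve.

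- **Section 5.10.3, general rule.** For a patient who receives no valve: "Patient will then be withdrawn from the study". The listed reasons include both procedural exclusion and an unsuccessful implant attempt.
- **Section 5.10.3, exception.** It applies "if the Portico valve or delivery system entered the patient's body but was not successfully implanted". That patient should "continue in follow-up until 30 days or until all adverse events associated with the Portico device or procedure are resolved (whichever occurs first".
- **Section 6.2.3, Procedural Exclusion.** "Any patient that does not have a delivery system enter his or her body will be considered" procedurally excluded. For this group the section says: "Data will be collected on these subjects from the Baseline through the 30-day follow-up". Withdrawal comes only after that.
- **Section 7.3.2.** Safety surveillance and reporting "will continue until the last investigational visit has been performed or the patient is deceased or the patient/investigator concludes his participation". A note there adds that, for an adverse event documented at the last follow-up visit, the sponsor is to receive follow-up information as well as the notification.

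The secondary objective in section 5.2.2 is to "assess the peri-procedural and long-term performance and safety profile of the Portico Valve implanted, using the Delivery System and the Loading System".

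**The concern.** The exception in 5.10.3 makes the length of follow-up depend on the patient's own adverse-event course. Once the related events have resolved, the patient may leave, and nothing then obliges the site to report a bleed, stroke or death that begins later but still within 30 days. Data collected this way cannot support a uniform 30-day rate for failed attempts, because observation time differs between patients for a reason tied to outcome.

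The two sections also give different instructions for patients no delivery system entered: 6.2.3 collects data to the 30-day follow-up, while 5.10.3 places procedural exclusions among the patients withdrawn and gives no period. A site cannot tell which applies. If it follows 6.2.3, patients exposed to the delivery system can end up with less data than patients who were not.

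At stake is the peri-procedural safety record of the delivery system in attempts that failed after entry. No endpoint estimate is at stake.

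**Working it through.** The plan states no figure on this point, so the check sets the rules side by side.

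**1. The rules.** Let T be the day on which the last device- or procedure-related adverse event resolves.

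| Patient | Section 5.10.3 | Section 6.2.3 |
|---|---|---|
| Valve or delivery system entered, not implanted | min(30, T) days | outside its definition of procedural exclusion |
| No delivery system entered | withdrawn, no period given | baseline through the 30-day follow-up |

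Section 6.2.5 sets the visit window: "The 30 Day visit will take place at 30days (-7 days, +14days) after the index procedure". That is day 30 − 7 = 23 to day 30 + 14 = 44, with nominal day 30.

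**2. What 5.10.3 does to a device-entered patient.**

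- *Related event resolves before day 30 (T < 30).* Follow-up may end at T. Under 7.3.2 the reporting duty ends with participation, so a new event between T and day 30 need not be captured. This is the clear gap.
- *No related event at all.* The text is ambiguous. Either the resolution condition is already met and the patient may leave at once, or there is nothing to resolve and the 30-day limit applies.
- *Related event open at day 30.* Scheduled follow-up ends at day 30. The event has already been reportable, and the note in 7.3.2 asks for follow-up information if it is documented at the last visit, but sets no duration.

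**3. Who is followed longer.**

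- *If 6.2.3 governs:* on nominal days min(30, T) never exceeds 30, and it is below 30 whenever T < 30. Exposed patients are then never followed longer than unexposed ones, and sometimes less.
- *If 5.10.3 governs alone:* unexposed patients are withdrawn and exposed patients are followed for up to 30 days, so the order reverses.

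The direction therefore depends on which section prevails. The early exit does not.

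**4. Illustration of the early exit (assumed inputs).** The documents give no resolution times. If T were exponential with mean m days, expected follow-up would be m × (1 − exp(−30/m)).

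| Assumed m (days) | Expected follow-up (days) | Share of 30 days |
|---|---|---|
| 3 | 3.0 | 10% |
| 7 | 6.9 | 23% |
| 14 | 12.4 | 41% |
| 30 | 19.0 | 63% |

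The number of patients is also not given. Assuming that 1% to 5% of the 866 planned for Cohort A have a failed attempt after device entry: 0.01 × 866 = 8.66, about 9; 0.05 × 866 = 43.3, about 43.

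**5. What does not move.** Section 5.10.3 keeps patients without a valve out of endpoint reporting, and sections 9.3 and 9.4 measure time from the implant date, which these patients do not have. Section 9.1 leaves procedural exclusions out of the analysis dataset. It does not name device-entered failures under the 6.2.3 definition, but the other two provisions already keep them out.

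**The case against.** The case on the other side has five parts.

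- **The sections may be compatible.** 5.10.3 could be giving the outcome (withdrawal) and 6.2.3 the timing (after 30 days). That is possible, but 5.10.3 presents continued follow-up as an exception for device-entered patients only, which implies that the others are not followed. If the sections are read together in this way, 6.2.3 governs and exposed patients are the ones who can have less data.
- **The comparison is conditional.** A reader might infer that exposed patients are simply followed less than unexposed ones. The documents do not support that outright: under 5.10.3 alone the reverse holds. This objection stands.
- **Open events are not lost.** A reader might infer that device-related harm unresolved at day 30 is discarded with no recorded outcome. Section 7.3.2 requires serious events and device effects during participation to be reported within 3 calendar days, and its note asks for follow-up information on an event documented at the last visit. Only the later course is uncertain. This also stands.
- **Deaths are reportable anyway.** Section 7.4.1 requires all patient deaths to be reported, but it does not clearly extend past withdrawal. It softens the gap for deaths and does nothing for other new events.
- **The plan is about implanted patients.** The objectives and endpoints concern patients who received a valve, so a 30-day rate for failed attempts is not something the plan promises. That is fair as to endpoints. Yet 5.2.2 names the delivery and loading systems, and safety data collected for separate reporting should not have follow-up that depends on outcome.

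**Conclusion.** Two defects hold on the text. First, 5.10.3 and 6.2.3 conflict on patients no delivery system entered. Second, 5.10.3 permits device-entered, non-implanted patients to leave before day 30 once related events have resolved, after which new events need not be captured. If 6.2.3 governs, exposed patients can have less data than unexposed ones.

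The primary endpoint and the implanted-patient endpoint set are unaffected. The loss falls on the separately reported peri-procedural safety data. Its size cannot be computed from the documents; the 9 to 43 patients and the follow-up shares of 10% to 63% rest entirely on assumed rates and resolution times.

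A reader might go further and conclude that early device harm is under-recorded. The documents show only that it could be: how often early exit would be used, and how often an event would follow it, is not stated. Exit on day 1 by a patient with no adverse event is likewise one reading of ambiguous wording.

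The change should be made, because the wording is unclear to sites and the repair is small.

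**What to change.** Replace the two provisions with one data-collection rule, worded the same in 5.10.3 and 6.2.3:

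1. Every patient in whom the procedure was started has adverse events and vital status collected through day 30, with no early exit on resolution of events, and is then withdrawn. State in the same place what counts as started.
2. For device- or procedure-related events still open at day 30, state that the note in 7.3.2 applies and that follow-up information is reported until the event is resolved or stable. Simply turning the earlier-of rule into a later-of rule would not do: an event that never resolves would then mean follow-up without end.
3. Tabulate the 30-day events of device-entered, non-implanted patients separately from the endpoint set.

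The cost is a change of wording in two sections, one added table, a 30-day contact for a small number of patients, and follow-up information on the few events still open at that point. Section 6.2.3 already asks for 30-day data on the less-exposed group, and no new procedure is needed.
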